8.8 Prior and concomitant therapy

Any prior or concomitant therapy that the patient may be taking and may be necessary for the patient's welfare taken within two weeks prior to the start of the study and during the study must be recorded in the patient's source documentation and in the CRF (including start/stop dates, dose frequency, route of administration, and indication).

The patient may be on a stable, continuous regimen of fiber, or probiotics one month before the Screening Visit; however, he/she must maintain a stable dose regimen through Week 12. Additionally, certain drugs used for the treatment of IBS (e.g. low dose tricyclic antidepressants) may be allowed at the discretion of the Medical Monitor provided the patient remains on a stable dose for one month prior to the Screening Visit and throughout the study with the exception of tegaserod, lubiprostone, linaclotide, metoclopramide, prucalopride, domperidone, plecanatide, CandiBactin, Atrantil, Allimax/Allimed within 2 weeks prior to the Screening Visit or antibiotics within 2 months prior to the Screening Visit.

Rescue medication will be allowed for severe constipation (i.e. when symptoms become intolerable). For guidance purposes for this protocol, intolerable symptoms may be when a subject has not had a complete spontaneous bowel movement (CSBM) in the preceding three days with an abdominal pain score of \geq 6 on an 11-point (0-10) scale each day during that time period. However, intolerability is ultimately a subjective judgment, and principal investigators and their patients make the final decision regarding what is intolerable and requires use of the rescue medication. For the Randomization Visit only, rescue medication will not be allowed the day before, the day of, or the calendar day after the Randomization Visit. If rescue medication is taken during this time, it must be recorded as a protocol deviation and the subject should not be randomized. The use of protocol-specified rescue medication and non-protocol-specified laxatives will be recorded in the subject record.

Permitted rescue medications include bisacodyl, magnesium citrate, magnesium hydroxide, and lactulose. Dosage and frequency should be followed according to package insert on rescue medication and should not exceed recommended doses as approved by package insert.

9. Procedures and variables

9.1 Schedule of assessments

Table 1: Schedule of assessments

X = required; O = only if directed by symptoms or reported AE; ET = early termination

Visit No.	1		2	3	4	5	EOS
Туре	Screen	Pre-treatment	Randomize				Call/Visit
Days	-17 to -14	-17 to -1	1	28	56	84 or ET	85
Window (Days)				±5	±5	±5	+1
Participant Information							
Informed Consent ¹	Х						
Inclusion/Exclusion ¹	Х						
IBS-C Criteria (ROME IV) ¹	Х						
Demographics ²	Х						
Medical History ³	Х		х				
Prior/Concomitant Medications	х		х	х	х	х	х
Diary compliance/ eligibility to randomize ⁴		х	х				
Physical							
Physical Exam ⁵	Х		Х	0	0	Х	0
Vital Signs ⁶	Х		Х	Х	Х	Х	0
12-Lead ECG ⁷	Х					Х	
Drug Dispensing							
Drug Dispensing			х	Х	Х		
Accountability/Returns				Х	Х	Х	
Adverse Events							
AEs			Х	Х	Х	Х	Х
Blood Samples							
Clinical Chemistry (CMP)	Х		Х	Х		Х	
Lipid Panel			Х			Х	
Cytokine Analysis			Х	Х		Х	
Hematology	Х					Х	
Serum Pregnancy ⁸	Х						
Creatine Kinase (CK)	Х			0	0	0	0
Urine Samples							

Urine Drug Screen	Х						
Urine Pregnancy ⁸			Х	Х	Х	Х	
Patient Reported							
Outcomes (REDCap)							
Diary Dispensing or	v					v	
Return ⁹	^					^	
Diary Compliance ¹⁰		Х	Х	Х	Х	Х	
EQ-5D-5L QoL			×			v	
Questionnaire ¹¹			^			^	
Stool Samples ¹²							
Bacteria (16S rRNA)			Х			Х	
Methanogens (qPCR)			Х			Х	
Breath Gases							
Lactulose breath test ¹³	Х					Х	
Single-point breath test			Х	Х	Х		

¹Informed consent, inclusion/exclusion criteria, and ROME IV may be reviewed and signed prior to Visit 1.

²Date of birth, gender, race/ethnicity.

³Patients will complete the information in the REDCap system during the Screening Period.

⁴Patients will be eligible for randomization if they fully respond to the PRO questions on at least 11 of 14 days.

⁵General examination, including head, ears, eyes, nose, throat, endocrine, cardiovascular, respiratory, abdomen, skin, neurological, extremities, and musculoskeletal features.

⁶Body weight, blood pressure (requires the patient to be semi-supine for at least 5 minutes prior to the test) height (Screening Visit only), radial pulse rate, respiratory rate, and temperature.

⁷12-lead ECG requires the participant to be supine for at least 5 minutes prior to the test.

⁸All female participants of child-bearing potential.

⁹Provide and train the patient to use the REDCap system with questionnaire.

¹⁰Ongoing review and confirmation of patient PRO questionnaire compliance. Patients will complete the information contained in the REDCap system each day, assessing stool frequency, SBMs, CSBMs, and use of rescue medication or other laxative use; stool consistency using the Bristol Stool Chart; abdominal pain assessment using visual NRS scale (0-10) and visual Likert scale (0-4) for straining and bloating assessment. Questionnaires will also be completed weekly for the PAC-SYM questionnaire and Adequate Relief question.

¹¹EQ-5D-5L questionnaire will be completed in the REDCap system on Day 1 prior to study drug administration and at Week 12 or upon early termination.

¹²Pre-treatment stool sample can be collected any time during the week preceding and including Day 1 and will only be analyzed if the patient is randomized into the study; Day 84 stool sample can be collected any time during the week preceding and including Day 84. ¹³Patients are fasted overnight prior to lactulose breath testing. Lactulose breath test measures hydrogen, methane, hydrogen sulfide, and carbon dioxide levels.

9.2 Timing of assessments

9.3 Assessment parameters

Subjects who provide written consent to participate will be screened for inclusion in the study. Consent to participate must be obtained prior to completing any study procedures and may be obtained prior to the Screening Visit.

9.3.1 ROME IV criteria

The investigator or designee will assess whether the subject meets the following ROME IV IBS criteria²⁸:

Subject has had IBS symptoms at least six months prior to diagnosis and is experiencing abdominal pain, on average, at least one day per week for the three months preceding the Screening Visit and associated with two or more of the following:

- Abdominal pain or discomfort related to defecation;
- Abdominal pain or discomfort associated with a change in frequency of stool; and/or
- Abdominal pain or discomfort associated with a change in form (appearance) of stool.

On symptomatic days, subject reports more than 25% of stools are Type 1 or 2 and less than 25% of stools are Type 6 or 7 on the Bristol Stool Form Scale.

In addition to the ROME IV criteria, subjects must meet the inclusion and exclusion criteria listed above.

9.3.2 Demographics and medical history

The study staff will record the subject's sex, date of birth, and ethnic origin.

Medical history findings (i.e. previous diagnoses, diseases or surgeries) meeting all criteria listed below will be collected:

- Not pertaining to the study indication;
- Start before signing of the informed consent;
- Considered relevant to the study;
- Differentiated from adverse events.

Findings will be recorded in REDCap via the medical history questionnaire (Appendix 13.6).

9.3.3 Physical exam

Complete physical exams will be performed during the Screening Visit and Visits 2 and 5 by the investigator or a physician co-investigator. The general examination will include evaluation of the head, ears, eyes, nose, throat, endocrine, cardiovascular, respiratory, abdomen, skin, neurological, extremities, and musculoskeletal systems. Abnormalities noted at the Screening Visit will be recorded as medical history. Any clinically significant change from the Screening Visit will be recorded as an adverse event.

9.3.4 Vital signs

Vital sign measurements, including body weight, blood pressure, radial pulse rate, respiratory rate, and temperature will be recorded at all clinic visits except the End-of-Study Call/Visit. Vital signs will be collected after the subject has been semi-supine for at least five minutes prior to the test. Height will be recorded at the Screening Visit only.

9.3.5 12-lead ECG

A standard 12-lead ECG will be performed by a trained research nurse during the Screening Visit and Visit 5. ECGs will be interpreted by a trained cardiologist.

9.3.6 Blood draw

Blood will be drawn by a trained research nurse and collected for hematology, clinical chemistry, lipid, cytokine, and creatine phosphokinase. Laboratory analyses will be performed in the central clinical laboratory and MAST research laboratory at Cedars-Sinai Medical Center. Reference ranges will be supplied by the clinical laboratory and used by the investigator to assess the laboratory results for clinical significance and pathological changes. Blood samples will be used for serum pregnancy tests in women of childbearing potential.

Clinical chemistry (CMP) will be assessed on Visits 1 (Screening Visit), 2, 3, and 5. Creatine kinase (CK) will be assessed during Visit 1, however may be assessed as needed during the remaining study visits as indicated by the development of symptoms suggestive of myopathy and/or rhabdomyolysis.

Blood will be drawn during all visits except Visit 4 and the End-of-Study Call/Visit; however, blood may be drawn on Visit 4 and/or the End-of-Study Call/Visit as dictated by occurrence of subject symptom or adverse events.

9.3.7 Urine samples

Subjects will be asked to provide up to one cup of urine for drug and toxicology analysis during the Screening Visit. Urine samples will also be collected for pregnancy tests from women of childbearing potential during Visits 2, 3, 4 and 5.

9.3.8 Daily diary and questionnaires

A study diary will be completed each day assessing stool frequency, SBMs, CSBMs, and the use of rescue medication (Appendix 13.3). Stool consistency will be assessed using the Bristol Stool Chart (Appendix 13.2). Severity of abdominal pain Will be assessed via visual NRS scale (0-10), while severity of bloating and straining will be assessed via Likert scale (0-4)

The PAC-SYM questionnaire and adequate relief question (Appendix 13.4) will be completed weekly. The EQ-5D-5L questionnaire (Appendix 13.5) will be completed on Day 1 prior to study drug administration and at Week 12 or upon early termination.

Subjects will be instructed on how to use REDCap to complete the assessments. During the Screening and Pre-treatment Period, subjects must complete the daily assessment for at least 14 days and have full responses to the questions on 11 or more of the 14 days before the start of the Treatment Period.

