13.3 Daily questionnaire

Did you have a bowel movement today?

If yes, did it feel complete?

What did it look like? Please use the Bristol Stool Chart as a reference.

Did you have more than one bowel movement today?

If yes, did it feel complete?

What did it look like?

Did you have more than two bowel movements today?

If yes, did it feel complete?

What did it look like?

Did you take a laxative today?

Date: June 30. 2020	Version: 8.0	Page: 46 of 52

If yes, please specify: Protocol-recommended rescue medication (bisacodyl, magnesium citrate, magnesium hydroxide, or lactulose) or Other laxative (oral, suppository, or enema)

If other, please specify the name of the laxative taken.

How severe has straining been during your bowel movements over the last 24 hours.

- 0 None (absent)
- 1 Mild (not very severe)
- 2 Moderate (somewhat severe)
- 3 Severe
- 4 Very Severe

Using the scale above, please rate the worst level of abdominal pain you have felt over the past 24 hours.

Bloating is a condition in which the belly (abdomen) feels full and tight or may look or feel swollen/distended. Patients may experience abdominal fullness, pressure, or a sensation of trapped gas.

Please rate the worst level of bloating you have felt over the last 24 hours.

- 0 None (absent)
- 1 Mild (not very severe)
- 2 Moderate (somewhat severe)
- 3 Severe
- 4 Very Severe

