#### 3. ENDPOINTS

#### 3.1. PRIMARY EFFICACY ENDPOINT

The primary efficacy endpoint is the change from baseline in the weekly average number of complete spontaneous bowel movements [CSBMs] during the 12-week Treatment Period.

A CSBM is a spontaneous bowel movement [SBM] that is associated with a sense of complete evacuation. An SBM is a bowel movement that occurs in the absence of rescue medicine use or other laxative use (e.g. suppository or enema) on the calendar day of bowel movement or the calendar day before the bowel movement.

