#### 6.2. BASELINE AND STUDY DAY DEFINITIONS

Baseline definition will vary upon the data/variables for summaries/analyses.

Table 1: Baseline Definitions

Data/Variables	Baseline Definition
Laboratory, vital signs, and ECG	The last non-missing value prior to the first dose of the study drug
Breath CH 4 AUC measurement	AUC of breath CH 4 measurements collected during lactulose breath test performed at Screening after an overnight fast
Singe-point breath CH 4 measurement	A single-point breath CH 4 measurement collected at Randomization after an overnight fast
Weekly average score for worst abdominal pain in the past 24 hours	(Sum of daily pain scores) / (number of days with pain score assessment during the 7 days prior to the first dose of study drug)
Stool frequency of CSBMs per week/Weekly average number of CSBMs	7 x (sum of daily number of CSBMs) / (number of days with CSBM assessment

	during the 7 days prior to the first dose of study drug)
Stool frequency of SBMs per week/Weekly average number of SBMs	7 x (sum of daily number of SBMs) / (number of days with SBM assessment during the 7 days prior to the first dose of study drug.
Weekly average of bloating score	Sum of daily bloating scores / (number of days with bloating score assessments during 7 days prior to the first dose of study drug)
Weekly average of straining score	Sum of daily straining scores / (number of days with straining score assessments during 7 days prior to the first dose of study drug)
Adequate Relief	The last non-missing value prior to the first dose of the study drug
Weekly stool consistency score (BSFS)	Sum of (i $\times$ number of type i stools) / total number of stools during 7 days prior to the first dose of study drug, where stool consistency i = 1, 2,7
EQ-5D-5L score	The last non-missing value prior to the first dose of the study drug

Study day will be defined as follows:

- The first dose of study drug is designated as Day 1.
- For visit days after Day 1, study day = visit date Day 1 date + 1.
- For visit days prior to Day 1, study day = visit date Day 1 date. Thus, study days for screening visit are negative numbers. There is no "Day 0".

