# 8.2. SECONDARY AND EXPLORATORY EFFICACY ENDPOINTS AND ANALYSIS

# 8.2.1. Secondary Efficacy Endpoints

The secondary efficacy endpoints are listed below:

- The proportion of overall responders during the 12-week Treatment Period (overall 12-week responders).
- Proportion of overall stool frequency responders during the 12-week Treatment Period.
- Proportion of overall abdominal pain intensity responders during the 12-week Treatment Period.
- Proportion of overall bloating responders during the 12-week Treatment Period.

• Proportion of patients using rescue medication.

The comparisons of the proportions will be performed using the Chi-squared test for equal proportions based on the full analysis set. The Chi-squared test from SAS Proc Freq will be used for the comparison of the treatment differences (each SYN-010 dose group versus placebo). Nominal P-values and 95% Newcombe-Wilson CIs for treatment differences will be presented.

To control the overall false positive rate, a fixed sequence testing procedure will be used for the testing of the secondary endpoints listed above. Specifically, the secondary endpoints will be tested formally if statistical significance is achieved for the primary endpoint for both dose groups, otherwise, the secondary endpoints will not be tested formally. If statistical significance is achieved for the primary endpoint for both dose groups, then the secondary endpoints will be tested formally in the order of the list for the 42 mg dose. The first listed secondary endpoint will be tested at the 2-sided alpha = 0.05 level. If statistical significance is not achieved, then the testing procedure will stop. If statistical significance is achieved for the first listed secondary endpoint, then the following secondary endpoint will be tested at the 2-sided alpha = 0.05 level. The testing procedure will continue for the testing of the secondary endpoints until statistical significance is not achieved for a secondary endpoint for the 42 mg dose group. If statistical significance is achieved for all listed secondary endpoints of the 42 mg dose group, then the testing procedure will be repeated for the 21 mg dose group.

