## 9.7. RESCUE MEDICATION

The number and percentage of subjects using protocol-specified rescue medication at any time post-baseline will be summarized by treatment.

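### Pre-treatment laxative use is collected daily but is neither tabulated by arm nor used in the rescue-medication comparison, which loses precision and interpretability

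*Protocol*

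**What the plan says.** **Collection.** Protocol 9.3.8: "A study diary will be completed each day assessing stool frequency, SBMs, CSBMs, and the use of rescue medication". Before treatment, "subjects must complete the daily assessment for at least 14 days and have full responses to the questions on 11 or more" of those 14 days. The daily questionnaire (Protocol 13.3) asks "Did you take a laxative today" and separates protocol rescue products from other laxatives. Protocol 8.8 adds: "The use of protocol-specified rescue medication and non-protocol-specified laxatives will be recorded in the subject record". The same section bars rescue medication only on the day before, the day of and the day after the Randomization Visit, so earlier pre-treatment use is possible and would be captured.

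**Indirect use.** SAP 3.1: "An SBM is a bowel movement that occurs in the absence of rescue medicine use or other laxative use" on the same or the previous calendar day. CSBMs are a subset of SBMs. Pre-treatment laxative use therefore affects baseline SBM and CSBM frequency (SAP 6.2, Table 1), the covariate in the primary ANCOVA (SAP 8.1) and the stool-frequency eligibility criterion (Protocol 7.2.1).

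**The rescue endpoint.** The proportion using rescue medication is the fifth of five sequenced secondary endpoints in SAP 8.2.1. The test is stated as: "The comparisons of the proportions will be performed using the Chi-squared test for equal proportions based on the full analysis set". SAP 9.7: "The number and percentage of subjects using protocol-specified rescue medication at any time post-baseline will be summarized by treatment". Laxative use has no row in Table 1 and no place among the baseline characteristics (SAP 7.2) or the subgroups (SAP 8.3). Prior medications are defined (SAP 7.4.1), but a summary is specified only for concomitant ones (SAP 7.4.2).

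**The concern.** The SAP otherwise relates its outcomes to baseline: the continuous endpoints carry their baseline as a covariate, and the other four sequenced secondaries are defined by change from baseline. Rescue use is the exception, although its baseline is already in the diary.

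Earlier laxative use is a plausible predictor of later rescue use. If it is prognostic, two things follow. The difference between prior users and non-users stays in the variance of the comparison and lowers power. And with randomization in blocks of 6 and no stratification described (Protocol 8.1), the arms may differ by chance in prior users. With no by-arm table, nobody reading the rescue result could tell whether that had happened.

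**Working it through.** **1. The plan's own power figure.** The documents power only the primary endpoint: difference 1.5 − 0.5 = 1.0, SD 1.5, 50 per arm, two-sided 5%. Noncentrality = 1.0 / (1.5 × √(2/50)) = 3.33, which gives 91.0% by the t-test, against 90% stated. It reproduces. No figure is given for rescue use, so every rate below is an assumption.

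**2. Chance imbalance in prior users, 50 per arm.** With prevalence q, the SD of the between-arm difference is √(2q(1−q)/50). Exact binomial probabilities:

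| Assumed q | SD of difference | Difference ≥10 points | Difference ≥20 points |
|---|---|---|---|
| 10% | 6.0 points | 13% | 0.2% |
| 30% | 9.2 points | 33% | 3.8% |
| 50% | 10.0 points | 37% | 5.7% |

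A 10-point imbalance shifts the observed difference in rescue use by 10% of the user/non-user contrast. With on-study use of 80% in prior users and 40% in non-users, that is 0.10 × 40 = 4 points.

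**3. Example effect size.** Take an odds ratio of 0.35 in both strata. For 80%: odds 4.00 × 0.35 = 1.40, so 58.3%. For 40%: odds 0.667 × 0.35 = 0.233, so 18.9%. With half prior users, placebo use is 60.0% and active use 38.6%, a difference of 21.4 points.

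**4. Power, unadjusted Chi-squared v Cochran-Mantel-Haenszel (CMH).** The CMH statistic, without continuity correction, is [Σ(a − n₁m/N)]² / Σ[n₁n₀m(N−m)/(N²(N−1))], summed over the two strata. Here a is the number of rescue users on active treatment, n₁ and n₀ the arm sizes, m all rescue users and N the stratum total. With 200,000 simulated trials per cell, 50 per arm and odds ratio 0.35, power in % is:

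| Placebo use, prior users / non-users | q = 10% | q = 30% | q = 50% |
|---|---|---|---|
| 75% / 45% | 66.9 v 67.9 | 66.6 v 68.1 | 67.2 v 68.8 |
| 80% / 40% | 61.5 v 64.3 | 59.5 v 64.6 | 59.8 v 64.9 |
| 85% / 35% | 54.8 v 59.5 | 50.2 v 59.4 | 49.5 v 59.2 |
| 90% / 25% | 40.1 v 48.0 | 32.2 v 47.7 | 32.1 v 47.5 |
| 60% / 60% (not prognostic) | 75.3 v 73.5 | 75.2 v 73.5 | 75.5 v 73.7 |

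The gain runs from about 1 to about 15 points. The last row shows a loss of about 2. A different set of assumptions (a fixed 20-point reduction, 30 to 50% prior users, placebo use 60 to 80% in prior users and 20 to 30% in non-users) gives gains of about 3 to 15 points, and 54% v 53% when prior use is not prognostic.

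**5. Type I error.** With odds ratio 1 in the same cells: 5.0 to 5.7% unadjusted, 4.8 to 5.1% CMH.

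**6. Trials with an unfavourable imbalance.** At q = 50%, the active arm has at least 10 points more prior users in about 18% of trials. Within those trials:

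| Placebo use | Power, unadjusted v CMH | Rejection under no effect |
|---|---|---|
| 80% / 40% | 36% v 64% | 7.7% v 5.1% |
| 85% / 35% | 20% v 57% | 9.1% v 5.1% |

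**The case against.** **The planned test is not wrong.** A reader might infer that chance imbalance biases the comparison or inflates its error rate. It does not: averaged over randomizations the unadjusted test stays near 5%, and its P-value and interval already allow for chance imbalance. Protocol 6.6 and SAP 8.2.1 agree on this test and promise no adjustment. This objection stands, and it limits the point to precision and interpretability.

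**Laxative data are not ignored.** A reader might infer that pre-treatment use enters no analysis. SAP 3.1 rules that out, because laxative use determines SBMs and CSBMs and hence the primary covariate. The rescue comparison, however, uses neither that covariate nor any other.

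**Little formal weight.** A reader might infer that a formal claim is directly at risk. Under SAP 8.2.1 rescue use is tested for 42 mg only after the primary succeeds for both doses and four earlier 42 mg secondaries succeed. For 21 mg, all five must first succeed at 42 mg and four again at 21 mg. The powers above are conditional on the test being reached. Nominal P-values and confidence intervals are still reported in every case.

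**Unsupported rates.** Protocol 7.2.2 excludes laxative abuse, over-the-counter laxatives within 3 days before Screening and several IBS-C drugs within 2 weeks before it. Rescue is meant for intolerable symptoms (Protocol 8.8). A 50% prevalence of prior use may therefore be too high. At 10% the gains are about 1, 3, 5 and 8 points. The largest gains also need strong user/non-user contrasts for which the documents offer no evidence.

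**Conclusion.** The point holds as a matter of efficiency and interpretability. A baseline measure bearing directly on a sequenced secondary endpoint is collected, then neither shown by arm nor used in that endpoint's comparison. The documents do not support calling the planned test invalid, saying that laxative data are unused throughout, or saying that a formal claim is likely to turn on it.

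Assuming 50 per arm, 10 to 50% prior users and an odds ratio of 0.35, stratification changes power by about +1 to +15 points as prior use becomes more prognostic, and by about −2 points if it is not prognostic. The documents fix none of these rates, so the gain is a range and not an estimate. The case for tabulating prior use by arm does not depend on them.

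**What to change.** Make these changes before unblinding, by staff who have not seen the interim results:

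- **SAP 6.2, Table 1:** define baseline laxative use (yes/no) from the pre-treatment diary. Use the same medication definition as the outcome (SAP 9.7 counts protocol-specified rescue medication only) or justify a broader one. State the diary window, noting that the other diary baselines use 7 days and that rescue is barred on the day before the Randomization Visit. State whether the SAP 6.4 rule that an unanswered question means no use also applies here. Full responses are needed on only 11 of 14 days, so that rule could classify some users as non-users.
- **SAP 7.2:** tabulate baseline laxative use by arm.
- **SAP 8.2.1:** compare rescue use for each dose with placebo by a Cochran-Mantel-Haenszel test stratified by this variable, with a stratified risk difference and 95% CI. Keep the unadjusted Chi-squared test and Newcombe-Wilson interval as supportive.

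The cost is SAP wording and a little programming, with no new data. The downside is a power loss of about 2 points if prior use turns out not to be prognostic.
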